7.5.3 Key Secondary Efficacy Analysis

The key secondary efficacy endpoints (PFS, ORR) will be analyzed using ITT, FAS and PPS. The key secondary efficacy analyses will be conducted using the ITT set.

- Progression Free Survival (PFS): Time from randomization to either documented radiological progression (determined by the central imaging analysis facility) or death from any cause. Subjects alive and free of progression are censored at the last tumor assessment date when alive and free of progression were known.
- Objective Response Rate (ORR): Percentage of subjects with a Best Overall Response (determined by the central imaging analysis facility) of Complete Response (CR) or Partial Response (PR).

PFS will be analyzed using the same statistical methods that are used in the primary efficacy analysis of OS.

ORR will be analyzed using the Cochran-Mantel-Haenszel test stratified by the randomization stratification factors Geographic region (Asia vs. North America/Europe), Prior ramucirumab treatment (Yes vs. No), and Treatment therapy line (3rd vs. ≥ 4th). For the ORR, the frequency and percentage (with 95% CI) of subjects will also be provided.

Data will be summarized in the following tables and figures.

-Table. Progression Free Survival [Independent Central Review] – ITT

-Table. Progression Free Survival [Independent Central Review] – FAS

-Table. Progression Free Survival [Independent Central Review] – PPS

-Figure. Kaplan Meier Plot for Progression Free Survival [Independent Central Review] - ITT

-Figure. Kaplan Meier Plot for Progression Free Survival [Independent Central Review] - FAS

-Figure. Kaplan Meier Plot for Progression Free Survival [Independent Central Review] – PPS

-Table. Objective Response Rate [Independent Central Review] – ITT

-Table. Objective Response Rate [Independent Central Review] – FAS

-Table. Objective Response Rate [Independent Central Review] – PPS

-Table. Progression Free Survival - [Investigator Review] – ITT

-Table. Progression Free Survival - [Investigator Review] – FAS

-Table. Progression Free Survival - [Investigator Review] – PPS

-Table. Objective Response Rate - [Investigator Review] – ITT

-Table. Objective Response Rate - [Investigator Review] – FAS

-Table. Objective Response Rate - [Investigator Review] – PPS

- List. Time to Event Parameters by Subjects – ITT Set

- List. Objective Response by Subject – ITT Set

7.5.4 Other Secondary Efficacy Analysis

All other secondary efficacy endpoints will be analyzed in the ITT, FAS, and PPS using two-sided test at the alpha=0.05 level of significance, with no adjustments for multiplicity.

- Disease Control Rate (DCR): Proportion of subjects with a Best Overall Response (determined by the central imaging analysis facility) of complete or partial response (CR or PR), or stable disease (SD).
- Global health status/quality of life score according to European Organisation for Research and Treatment of Cancer Quality of Life Questionnaire-Core 30 (EORTC QLQ-C30) and EORTC QLQ-STO22.
- Each dimension response according to EuroQol 5-Dimension 5-Level (EQ-5D-5L) Questionnaire.

For the DCR, the same statistical method that is used in ORR will be performed.

Each derived score from the European Organisation for Research and Treatment of Cancer Quality of Life Questionnaire-Core 30 (EORTC QLQ-C30) and EORTC QLQ-STO22 will be summarized by descriptive statistics by treatment group for each cycle. Each derived score from EORTC QLQ-C30 and EORTC QLQ-STO22 will also be analyzed using analysis of covariance (ANCOVA) models for each cycle with the derived change from baseline score as dependent variable, treatment group and the randomization stratification variables as factors, and the baseline score of the corresponding questionnaire as a covariate. Least

squares mean difference and 95% confidence interval with corresponding p-value for comparing two treatment groups will be presented.

For EuroQol 5-Dimension 5-Level (EQ-5D-5L), the number and percentage (%) of subjects for each level of each dimension will be presented for each cycle for both treatment groups. EQ VAS data will be analyzed using analysis of covariance (ANCOVA) models for each cycle with the derived change from baseline score as dependent variable, treatment group as a factor and the randomization stratification variables, the baseline score of the corresponding questionnaire as covariates. Least squares mean difference and 95% Confidence interval with corresponding p-value for comparing two treatment groups will be presented.

Data will be summarized in the following tables.

- Table. Disease Control Rate [Independent Central Review] – ITT
- Table. Disease Control Rate [Independent Central Review] – FAS
- Table. Disease Control Rate - [Investigator Review] – ITT
- Table. Disease Control Rate - [Investigator Review] – FAS

- Table. EORTC QLQ-C30 [Parameter] – ITT
- Table. EORTC QLQ-C30 [Parameter] - FAS
- Table. EORTC QLQ-STO22[Parameter] – ITT
- Table. EORTC QLQ-STO22 [Parameter]- FAS
- Table. EQ-5D-5L [Parameter] – ITT
- Table. EQ-5D-5L [Parameter] – FAS

- List. EORTC QLQ-C30 – ITT Set
- List. EORTC QLQ-STO22 – ITT Set
- List. EQ-5D-5L – ITT Set

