### 8.3.6. Other Secondary Efficacy Analyses

The primary and key secondary endpoints will also be analyzed using the FAS and PP sets. All other secondary efficacy endpoints will be analyzed in the ITT, FAS, and PP sets using two-sided test at the alpha=0.05 level of significance, with no adjustments for multiplicity.

- Disease Control Rate (DCR): Proportion of subjects with a Best Overall Response (determined by the central imaging analysis facility) of complete or partial response, or stable disease.
- Global health status/quality of life score according to European Organization for Research and Treatment of Cancer Quality of Life Questionnaire-Core 30 (EORTC QLQ-C30) and EORTC QLQ-STO22.
- Each dimension response according to EuroQol 5-Dimension 5-Level (EQ-5D-5L) Questionnaire.

For the DCR, the same statistical method that is used in ORR will be performed.

The European Organization for Research and Treatment of Cancer Quality of Life Questionnaire-Core 30 (EORTC QLQ-C30), EORTC QLQ-STO22 and EuroQol 5-Dimension 5-Level (EQ-5D-5L) Questionnaire will be analyzed using analysis of covariance (ANCOVA) models with treatment group and the randomization stratification variables as factors, and the baseline value of the corresponding endpoint as a covariate.

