5.4 Patient Reported Outcome Secondary Endpoints

The following secondary endpoints will be analyzed based on patient reported outcomes.

- Global health status/quality of life score according to European Organisation for Research and Treatment of Cancer Quality of Life Questionnaire-Core 30 (EORTC QLQ-C30) and EORTC QLQ-STO22
- Each dimension response according to EuroQol 5-Dimension 5-Level (EQ-5D-5L) Questionnaire

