10.2 Summary Statistics

Summary statistics for continuous variables/endpoints will be presented with number of observations (n), mean, standard deviation (SD), median, minimum (min), and maximum (max). Summary statistics for categorical variables/endpoints will be presented with counts (n) and percents. Unless otherwise specified, denominator of percentage is number of subjects included in the analysis set by each group.

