10.4 Statistical Analysis Methods

For a between-group comparison of categorical data, a chi-square test will be basically used and when more than 20% of the table cells have expected frequencies that are less than 5, Fisher's exact test will be presented. For confidence intervals of proportion of categorical data, if more than 20% of the table cells have expected frequencies that are less than 5, then exact 95% CIs will be calculated, otherwise approximate 95% CIs will be calculated.

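### SAP 7.5.4 promises a test for the EQ-5D-5L dimension responses but specifies only by-cycle percentages, and its default denominator mixes attrition with health

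*SAP*

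**What the plan says.** - **Endpoint.** SAP 5.4 lists "Each dimension response according to EuroQol 5-Dimension 5-Level (EQ-5D-5L) Questionnaire" as a secondary endpoint. SAP 7.5.4 and Protocol 8.2.2 and 8.3.6 do the same. EQ VAS appears in no endpoint list, although both documents describe it as part of the instrument.
- **Commitment to test.** SAP 7.5.4 opens with "All other secondary efficacy endpoints will be analyzed in the ITT, FAS, and PPS using two-sided test at the alpha=0.05 level of significance", without multiplicity adjustment.
- **Plan for the dimensions.** SAP 7.5.4 states that "the number and percentage (%) of subjects for each level of each dimension will be presented for each cycle for both treatment groups". It names no model, effect measure, confidence interval or p-value for them.
- **Plan for the VAS.** The next sentence reads "EQ VAS data will be analyzed using analysis of covariance (ANCOVA) models for each cycle", and a least-squares mean difference, confidence interval and p-value follow.
- **Protocol method.** Protocol 8.3.6 says "EuroQol 5-Dimension 5-Level (EQ-5D-5L) Questionnaire will be analyzed using analysis of covariance (ANCOVA) models with treatment group", with the randomisation factors and the baseline value in the model. SAP 13, the table of changes from the protocol, has no entry for EQ-5D-5L.
- **Generic categorical rule.** SAP 10.4 says "For a between-group comparison of categorical data, a chi-square test will be basically used", with Fisher's exact test when cells are sparse.
- **Denominator.** SAP 10.2 sets a default that applies unless something else is specified: "denominator of percentage is number of subjects included in the analysis set by each group". SAP 7.5.4 specifies nothing else, and SAP 11.1.1 leaves missing efficacy values missing.
- **Collection.** Protocol Table 1 schedules the questionnaires before dosing on Day 1 of each cycle and at end of treatment, and not at the follow-up visits.

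**The concern.** There are two separate gaps.

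First, the analysis of a declared endpoint is not determined. The opening of 7.5.4 promises a test, the specific paragraph is descriptive, the protocol names ANCOVA, and SAP 10.4 would supply a chi-square. Chi-square ignores the order of the five levels, the randomisation factors and the baseline response. Two analysts working from this text could report different things, and the only EQ-5D-5L component with a specified model is not the listed endpoint.

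Second, the by-cycle percentages are hard to interpret. Subjects who have stopped treatment no longer answer but stay in the denominator. The five levels then do not sum to 100%, each level falls over time in both arms even when responders' health is constant, and unequal attrition creates a gap between arms that has nothing to do with health.

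**Working it through.** The documents give no numerical figure for EQ-5D-5L, so there is none to reproduce. The check is the arithmetic of the denominator.

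**Inputs**
- Arm sizes: about 459 subjects at 2:1, so 459 × 2/3 = 306 and 459 × 1/3 = 153.
- Cycle *c* Day 1 falls 28 × (*c* − 1) days after Cycle 1 Day 1. Cycle 3 is 56 days, or 56/30.4375 = 1.84 months. Cycle 5 is 112 days, or 3.68 months.
- Attrition proxy (assumption): exponential time to the last questionnaire. Fast case: median 2.6 v 1.8 months, the PFS figures of the prior phase III trial in Protocol 1.2. Slow case: 6.5 v 4.7 months, the OS figures of the same trial, used as medians.
- Responder health (assumption): 60% report a problem on a dimension and 40% report none, identical in both arms.

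**Formula.** Share answering = exp(−ln 2 × months / median). Percentage shown under SAP 10.2 = share answering × share of responders at that level.

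**Results, drug v placebo** (gaps from unrounded values)

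| | Answering | Any problem shown | Gap | No problems shown |
|---|---|---|---|---|
| Cycle 3, fast | 61.2% v 49.2% | 36.7% v 29.5% | 7.2 | 24.5% v 19.7% |
| Cycle 3, slow | 82.2% v 76.2% | 49.3% v 45.7% | 3.6 | 32.9% v 30.5% |
| Cycle 5, fast | 37.5% v 24.2% | 22.5% v 14.5% | 7.9 | 15.0% v 9.7% |
| Cycle 5, slow | 67.5% v 58.1% | 40.5% v 34.9% | 5.7 | 27.0% v 23.2% |

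With responders as the denominator, every row reads 60% v 60% and 40% v 40%. Under the SAP default the five levels of a dimension sum to the Answering column. In the fast case at Cycle 3 that is 61.2% and 49.2%.

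**Equal attrition.** With a median of 2.6 months in both arms the gap is zero, but any problem still falls from 60% at Cycle 1 to 36.7% at Cycle 3 with no change in health.

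**Masking.** In the fast case, a true responder difference of 45% v 55% at Cycle 3 would appear as 0.612 × 45 = 27.6% v 0.492 × 55 = 27.1%.

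**Can a comparison be informative?** The fast case leaves about 187 v 75 respondents at Cycle 3. By Whitehead's formula with assumed levels of 35/35/20/8/2%, a proportional-odds comparison has about 77% to 80% power for an odds ratio of 2.0, depending on direction and averaging. At 1.5 it has about 36%. Neither odds ratio comes from the documents.

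**The case against.** **The arms are never compared on this endpoint.** A reader might infer this from the descriptive paragraph. The documents do not support it: the opening sentence of 7.5.4 commits this endpoint to a test, and SAP 10.4 supplies a default for categorical data. What stands is that the method is not tied to the endpoint and drops features of the protocol's ANCOVA.

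**The table would make the drug look worse.** A reader might infer this from the any-problem column alone. The planned table shows every level, and no problems is inflated in the same proportion. The artefact favours neither arm. Nor do the percentages show attrition instead of health: they are the product of the two.

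**The default test would have an inflated error rate.** If a chi-square were run on analysis-set percentages, identical responder health (50% at a level) would be called different in about 26% of trials at Cycle 3 in the fast case and 9% in the slow case. Nothing says the test would be run that way, and a chi-square on observed responses would leave missing answers out.

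**The denominator is only a default.** The table shells in SAP Appendix 1 are listed but not shown and could set another one. Because counts are also presented, a reader could rebuild the responder distribution. Both points are fair. Neither puts the rule in the SAP text, which as it stands gives the analysis set.

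**Frequencies for ordinal items and ANCOVA for the VAS are a reasonable choice.** Protocol 8.3 leaves details to the SAP. That defends the choice, but not the conflict with 7.5.4's own opening or the missing entry in SAP 13, whose footnote exempts only grammatical and typographical changes.

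**Conclusion.** The point holds in a limited form. A test is promised for the EQ-5D-5L dimensions but not specified, the protocol's ANCOVA is narrowed to EQ VAS without being logged, and the stated default denominator mixes attrition with health in every by-cycle percentage.

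The size is illustrative: a false gap of about 3.6 to 7 points at Cycle 3 with 60% of responders reporting problems. It rests on exponential attrition, on another trial's OS or PFS figures as the proxy, and on attrition differing between arms. Treatment beyond progression (Protocol 6.3) could slow attrition, and equal attrition would remove the gap between arms, though not the decline over time.

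The endpoint lies outside the fixed OS–PFS–ORR sequence, so no confirmatory conclusion is affected. It should be corrected because it is a declared endpoint and correction is cheap.

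**What to change.** In SAP 7.5.4:

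1. Use subjects answering at that cycle as the denominator for the dimension levels, and show the numbers answering and expected by cycle and arm.
2. Name one comparison per dimension: either a proportional-odds model with treatment, the randomisation factors and baseline level, or a stratified Cochran-Mantel-Haenszel row-mean-score test. State that it is conditional on remaining on treatment, which a responder denominator does not cure, and that it is unadjusted for multiplicity.
3. Keep EQ VAS as supportive.

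In SAP 13, log the change from the protocol ANCOVA. If the table shells already set a responder denominator, say so in the SAP text.

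The cost is SAP wording, a few lines of code and five more unadjusted p-values per time point. No new data are needed.

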7.6 Pharmacodynamic Analysis

All pharmacodynamic parameters (VEGF, sVEGFR-2, sVEGFR-2, and sVEGFR-3) will be summarized by visit (baseline, completion of each 28-day cycle and end of treatment/discontinuation) and will also be listed. Summaries will include descriptive statistics including number of observations (n), mean, standard deviation (SD), median, minimum (min), and maximum (max).

All SNP data will be summarized with a table detailing the distribution of SNPs at baseline with the number of subjects and corresponding percentage of each polymorphism for each SNP analyzed (i.e. rs1870377, rs2305948, and rs17709898). Each SNP analyzed will also be listed for each subject.

- Table. Summary of Pharmacodynamic Factors – ITT
- Table. Summary of SNP Distribution – ITT

- List. Pharmacodynamic Factors – ITT
- List. Subject SNP Status – ITT

8. SAFETY EVALUATION

All safety evaluation is based on Safety Set and summarized by treatment group.

8.1 Extent of Exposure

To access the extent of exposure to the treatment, descriptive statistics will be presented for number of cycles, total cumulative dose (mg), duration of treatment (days), delivered dose intensity (mg/day) and relative dose intensity (RDI) by treatment group. Also, subjects with one or more dose interruptions, subjects with one or more dose adjustment and subjects off treatment will be summarized. The number of cycles will refer to all cycles started, including those discontinued or temporarily suspended.

Exposure related variables are defined as:

- The duration of treatment (days) = Date of last treatment admin.– Date of first treatment admin. +1
- Delivered Dose Intensity (mg/day) = Total dose delivered / The duration of treatment
- Relative Dose Intensity (RDI) = Delivered Dose Intensity (mg/day) / 700 mg/day

Data will be summarized in the following tables.

- *Table. Treatment Exposure – Safety Set*

- *List. Drug Concentration Data – Safety Set*

- *List. Subjects with Dose Adjustment – Safety Set*

8.2 Adverse Events

AEs will be coded by Preferred Term (PT) and System Organ Class(SOC) using version 19.0 or newer of Medical Dictionary of Regulatory Activities (MedDRA). All AE tables will reflect only TEAEs defined in 5.6.2. Adverse events severity will be classified according to NCI-CTCAE (version 4.03). Adverse events that have relationship with investigational product such as certain, probable/likely, possible, conditional/unclassified or unassessable/unclassifiable will be defined as adverse drug reaction (ADRs).

8.2.1 Overall Summary of Adverse Events

The number of subjects, incidence rate with its 95% CI and number of events will be presented for TEAEs, adverse drug reaction (ADR) and serious adverse event by treatment group during the study. Chi-square test or Fisher's exact test will be used for comparison of AE incidence between groups.

Data will be summarized in the following tables.

- *Table. Overall Summary of TEAEs – Safety Set*

- *Table. Overall Summary of Serious TEAEs – Safety Set*

- *Table. Overall Summary of ADRs – Safety Set*

- *Table. Overall Summary of Serious ADRs – Safety Set*

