Statistical Methods	
Efficacy analysis
 
The primary analysis of OS will be conducted in the ITT population (all randomized subjects) using a stratified (by the randomization stratification factors) logrank test at the two-sided alpha=0.05 level of significance.
 
If the primary analysis of OS is statistically significant, then the key secondary endpoints of PFS and ORR will be analyzed using a fixed-sequence testing procedure. First, PFS will be analyzed using the same statistical methods that are used in the primary efficacy analysis of OS.
 
If the analysis of PFS is statistically significant, then ORR will be analyzed using the Cochran-Mantel-Haenszel test stratified by the randomization stratification factors. However, if a prior test is not statistically significant, then the subsequent analyses will be exploratory rather than confirmatory.
 
All other secondary efficacy endpoints will be analyzed using two-sided tests at the alpha=0.05 level of significance, with no adjustments for multiplicity DCR will be analyzed using the same methodology as described for ORR.
 
For the European Organization for Research and Treatment of Cancer Quality of Life Questionnaire-Core 30 (EORTC QLQ-C30) and EuroQol 5-Dimension 5-Level (EQ-5D-5L) Questionnaire, the treatment groups will be compared using analysis of covariance (ANCOVA) models with treatment group and the randomization stratification variables as factors, and with the baseline value of the corresponding endpoint as a covariate.
 
Safety analysis
 
Safety parameter data will be summarized and listed by patient. Summary tables will show incidence rates (number of subjects with at least one event) of AE, SAE, etc., as well as summaries of severity (CTCAE v4.03) and causal relationship. Change from baseline tables will be presented for clinical laboratory assessments, vital signs and ECOG performance score. Laboratory abnormalities will also be

	summarized in tables showing shifts in grade.

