### **3) Phase III clinical study in patients with advanced or metastatic gastric cancer**

A multicenter, randomized, double-blind, phase III study was conducted in patients who failed to second-line therapy. The study was designed as 28 days/cycle, consisting of YN968D1 850 mg (as apatinib mesylate) group and Placebo group. The primary efficacy endpoint was overall survival. Randomization was done centrally and was stratified by the number of metastatic sites ( $\leq 2$  or  $> 2$ ). A total of 267 randomly assigned subjects were included in FAS population; 176 in the YN968D1 group and 91 in the Placebo group. As for the efficacy, mean overall survival was statistically greater for the YN968D1 group than for the Placebo group (6.5 months versus 4.7 months; HR= 0.709; 95% CI (0.537~0.937);  $p < 0.0149$ ). mPFS also showed the same result (2.6 months versus 1.8 months; HR= 0.444, 95%CI (0.331~0.595),  $P < 0.001$ ). ORR was 2.84% and 0.00% for the YN968D1 group and the Placebo group, respectively. As for the safety, YN968D1 was mostly controlled by treatment discontinuation or reduction. The most common adverse events were hand-foot skin reaction (HFSR), proteinuria and hypertension. In conclusion, the efficacy and safety of YN968D1 850 mg were confirmed in advanced and metastatic gastric cancer.

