### 5.3. Safety Assessment

#### 5.3.1. Adverse Event

Assessments will be made on the adverse events (AEs) including any sign, symptom, disease or illness that occurred newly or if present at baseline, worsened in a subject and may impair the well-being of the subject. Clinical laboratory findings and any other findings from the diagnostic procedures that are considered clinically significant (e.g. requiring unscheduled diagnostic procedures or treatment modalities or resulting in discontinuation of the study) will also be included in the AE assessment.

AEs will be collected and evaluated at each visit after informed consent is signed until 28 calendar days after the last administration of the investigational product. Any AEs that emerged following administration of IP will be evaluated in comparison to the baseline level of AEs determined at screening.

See [Section 7](#) for detailed information on **SAFETY REPORT** of this study.

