5.9.2 Treatment-Emergent Adverse Events

Treatment-emergent adverse events (TEAEs) are defined as AEs that have a start date on or after the first dose of the investigational product until the final subject visit or, if it has a start date before the date of the first dose of study drug, increase in severity on or after the date of the first dose of investigational product until the final subject visit. If there are partial or missing dates, the imputation algorithm in Section 11.3 will be followed to decide whether the AE is TEAE.

Adverse events collected during screening period (from the time-point of informed consent until right before the first administration of the investigational product) will be separately listed and reviewed.

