8.2.2 Display of Adverse Events

All TEAEs and ADR will be presented according to standardized SOC and PT. The following conventions will be used in summarizing AEs:

- For subject incidence summaries, a subject will be counted only once within each SOC and within each PT.
- Summaries by NCI-CTCAE grade – if a subject reports more than 1 AE within an SOC and/or PT, the AE with the highest severity within each SOC and within each PT will be included.
- When the number of events is calculated, more than 1 AE counted as different events

Data will be summarized in the following tables and listings.

- *Table. Incidence of TEAEs by SOC and PT – Safety Set*
- *Table. Incidence of ADRs by SOC and PT – Safety Set*
- *Table. Incidence of TEAEs by the Worst NCI-CTC Grade, SOC and PT [Rivoceranib + BSC] – Safety Set*
- *Table. Incidence of TEAEs by the Worst NCI-CTC Grade, SOC and PT [Placebo + BSC] – Safety Set*
- *Table. Number of TEAEs by NCI-CTCAE, SOC and PT [Rivoceranib + BSC] – Safety Set*
- *Table. Number of TEAEs by NCI-CTCAE, SOC and PT [Placebo + BSC] – Safety Set*
- *Table. Incidence of ADRs by the Worst NCI-CTC Grade, SOC and PT [Rivoceranib + BSC] – Safety Set*
- *Table. Incidence of ADRs by the Worst NCI-CTC Grade, SOC and PT [Placebo + BSC] – Safety Set*
- *Table. Number of ADRs by NCI-CTCAE, SOC and PT [Rivoceranib + BSC] – Safety Set*
- *Table. Number of ADRs by NCI-CTCAE, SOC and PT [Placebo + BSC] – Safety Set*
- *List. Subjects with TEAEs – Safety Set*

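### SAP 8.2.1 tests crude adverse-event incidence although each subject's observation window depends on when treatment stops; if placebo subjects stop earlier, events the drug does not cause can look more frequent on active

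*SAP*

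**What the plan says.** SAP 8.2.1 covers four overall tables: any treatment-emergent AE (TEAE), serious TEAEs, adverse drug reactions (ADRs) and serious ADRs. It gives subjects, incidence with 95% CI and number of events, and adds that "Chi-square test or Fisher's exact test will be used for comparison of AE incidence between groups". SAP 10.4 sets the choice of test: chi-square by default, and "when more than 20% of the table cells have expected frequencies that are less than 5, Fisher's exact test will be presented".

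Incidence is crude. The Protocol synopsis speaks of "incidence rates (number of subjects with at least one event", and in the SAP 8.2.2 tables by system organ class (SOC) and preferred term (PT), "a subject will be counted only once within each SOC and within each PT". Neither involves person-time.

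Under Protocol 5.3.1, AEs are collected "until 28 calendar days after the last administration of the investigational product". The synopsis has treatment continue to progression, intolerable toxicity or withdrawal of consent, and Protocol 6.3 allows treatment beyond progression with supplemental consent.

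SAP 8.1 summarises exposure separately and descriptively: "The duration of treatment (days) = Date of last treatment admin.– Date of first treatment admin. +1". Nothing in SAP 8.2.1 to 8.2.3, or elsewhere in the SAP, relates AE counts to time at risk, analyses time to first event, or restricts both arms to a common period.

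SAP 5.9.2 closes the TEAE window at a different point from Protocol 5.3.1. It counts events with a start date "on or after the first dose of the investigational product until the final subject visit".

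**The concern.** A subject watched for longer has more time to have an event. Here the watching time is set by when treatment stops, and treatment usually stops at progression, which the drug is meant to delay. A crude comparison of proportions therefore mixes two things: the drug changing the event rate, and the drug changing the length of observation.

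The documents give reason to expect unequal windows. In the earlier phase III trial, "mPFS also showed the same result (2.6 months versus 1.8 months", with a hazard ratio of 0.444. In the phase II trial median PFS was 3.67 and 3.20 months on the two active regimens and 1.40 on placebo. PFS superiority is also the second confirmatory hypothesis in this trial.

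Safety evaluation is a stated aim. Of the four tables, the serious-TEAE comparison is the most exposed: much of what it counts can be background disease, and it is unlikely to sit near 100%. The same mechanism can hide a true benefit. With a placebo rate of 0.10 per month, a 25% lower rate on active and the phase III medians, crude incidence is 27.6% on placebo and 27.2% on active.

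**Working it through.** The plan states no power or error rate for the AE comparison, so there is no figure to reproduce.

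**Inputs.** About 459 subjects at 2:1, so 306 v 153, assuming nearly all are dosed. Two-sided 5%. AE window = time on treatment + 28 days (0.92 month). Assumptions, not in the documents: exponential time on treatment with PFS medians as proxy, and the same constant event rate r in both arms (no drug effect).

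**Formulas.** With L = ln 2 / median, the mean window is 1/L + 0.92 and crude incidence is 1 − exp(−0.92r) × L/(L + r).

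**Phase III medians.** Placebo L = 0.6931/1.8 = 0.3851 and active L = 0.6931/2.6 = 0.2666. The mean windows are 3.5 and 4.7 months.

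Worked case, r = 0.10, exp(−0.092) = 0.912:
- placebo: 1 − 0.912 × 0.3851/0.4851 = 27.6%
- active: 1 − 0.912 × 0.2666/0.3666 = 33.7%
- pooled 31.6%; SE = √(0.316 × 0.684 × (1/306 + 1/153)) = 0.046
- expected z = 0.061/0.046 = 1.32, so rejection is about P(Z > 1.96 − 1.32) = 26%

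Simulated two-proportion tests agree:

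| r per month | Placebo | Active | Rejection at nominal 5% |
|---|---|---|---|
| 0.05 | 15% | 20% | 18% |
| 0.10 | 28% | 34% | 26% |
| 0.15 | 37% | 44% | 29% |
| 0.30 | 57% | 64% | 31% |

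Nearly all rejections point against active.

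**Other exposure gaps, same four rates.**

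| Active v placebo median (months) | Source | Rejection |
|---|---|---|
| 4.05 v 1.8 | 1.8/0.444, from the phase III hazard ratio | 75–91% |
| 3.20 v 1.40 | phase II | 67–90% |
| 2.19 v 1.8 | phase III plus an assumed toxicity stop rate of 0.05/month on active | 8–12% |
| 1.89 v 1.8 | the same at 0.10/month | about 5% |
| 1.8 v 1.8 | equal exposure | 5% |
| 1.5 v 1.8 | assumed shorter active exposure | 8–10%, nearly all against placebo |

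**Near-universal events.** At 97% placebo incidence, rejection is 8% with the phase III medians and 22% with 3.67 v 1.40.

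**Does the remedy work?** Comparing first events per patient-time at risk by a log rate ratio rejected in 4.2% to 5.8% of 4,000 simulated trials in every scenario run: medians 2.6 v 1.8, 4.05 v 1.8 and 3.67 v 1.40, with and without a quarter of windows ending in death. The crude test rejected in 13.6% to 98.2% of the same runs.

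**Limit of the remedy.** Let the event rate fall to a quarter of its initial value after month 1 (assumed), with the phase III medians and placebo incidence of 15% to 70%. The crude test then rejects in about 9–16%. The rate ratio rejects in about 9–19%, mostly in the opposite direction, because the longer active window adds low-rate time. A log-rank test on time to first event stays at 5%.

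**The case against.** The strongest reply is that the exposure gap is assumed. Nowhere do the documents say placebo subjects stop earlier. PFS is not time on treatment: active subjects can also stop for toxicity or a three-week dose gap (Protocol 6.2), and either arm may continue past progression (Protocol 6.3). This stands. Modest toxicity stopping removes most or all of the inflation, and shorter active exposure reverses it. It does not rescue the crude test, because the plan cannot know which case will occur.

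A reader might go further and conclude that events unrelated to the drug will often look drug-related. The documents do not support that. With the phase III medians a false signal is the minority outcome, and it becomes usual only with gaps like those in phase II or one implied by the hazard ratio of 0.444. A higher crude percentage is also not an attribution: ADR status rests on blinded investigator causality. Events confined to the first 28 days are essentially unaffected, since every survivor is observed that long.

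A reader might also carry the point to individual symptoms such as pain or bleeding, or to risk differences. SAP 8.2.2 and 8.2.3 name no test for SOC and PT rows. SAP 10.4 says which test to use when a comparison is made, without requiring one for each term. No AE risk difference is planned.

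Finally, event counts (8.2.1) and treatment duration (8.1) let a reader form an approximate rate, and no confirmatory decision rests on these p-values. Both are fair and limit the severity. But an approximate rate has no interval, uses all events rather than first events, and leaves out the 28 days after treatment.

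**Conclusion.** The point holds in conditional form. The AE window depends on outcome, the four overall comparisons in SAP 8.2.1 use crude incidence, and no planned analysis accounts for time at risk. If exposure follows the earlier phase III PFS medians and the event rate is constant, a nominal 5% test rejects in about 18–31% of trials with no drug effect, at placebo incidences of 15–57%. The figure rises with larger gaps and is about 5–12% if toxicity stops bring the active median to 1.9–2.2 months. It is lower for any-TEAE rates near 100% and 5% with equal exposure, and the bias runs against placebo if active exposure is shorter. The defect is certain from the text; its size and direction in this trial are not. It is a worthwhile, inexpensive improvement to the safety analysis and does not touch the primary efficacy result.

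**What to change.** In SAP 8.2.1, for the TEAE, serious TEAE, ADR and serious ADR summaries, add the number of subjects with a first event per patient-month at risk, with a rate ratio and 95% CI, and base the between-group comparison on it. Time at risk runs from first dose to the earliest of first event, death, data cut-off or the end of the TEAE window. Keep the crude percentages, and any chi-square or Fisher p-values, as descriptive only.

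First make the TEAE window the same for numerator and denominator. SAP 5.9.2 runs to the final visit and Protocol 5.3.1 to 28 days after the last dose. The end-of-treatment visit may be up to 7 days after the last dose (Protocol 3.4.4) and the post-treatment visit 28 ± 7 days after that (3.4.5), so the final safety visit can fall 7 + 28 + 7 = 42 days after the last dose. The two passages must be reconciled.

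The cost is SAP wording and a few table columns; the dates needed are already collected. The main drawback is that a single rate assumes a roughly constant hazard. Where onset is clearly front-loaded, a log-rank or Cox analysis of time to first event, from the same dates, is the check to report beside it.
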